4.6. Sampling and recruitment method

Patients will be included consecutively, in accordance with the inclusion/exclusion criteria previously established in sections 4.3 and 4.4 of this protocol. Inclusion will be carried out competitively without restrictions regarding the number of patients included in each center.

In accordance with the definition of the study population and disease established in this scientific report, patients will be selected from the diagnosed/treated cases of genitourinary tumors presenting with COVID-19 infection treated in the Spanish hospital centers participating in the study.

To prevent two or more doctors participating in the trial from registering the same case, a coordinator is designated, who controls the cases included in his center, in hospital centers with several participating doctors, and preventive measures are implemented in the tool that controls duplications. in the variables (such as age, sex, center or diagnosis).

4.7. Case definition

A "case" is defined as any patient, diagnosed, treated or followed up at the different hospital centers where physicians authorized by the sponsor are informed, who meets the inclusion criteria.

Medical care will be provided following applicable clinical criteria, in the context of routine clinical practice, regardless of the patient's inclusion in the study and following the best judgment of the specialists responsible for the patients.

4.8. Data Logging

Once data collection is possible (when the patient agrees to participate in the study through the informed consent procedure detailed in point 6.3 of this protocol, or after the waiver of consent has been requested and approved (RETROSPECTIVE PART ONLY) , medical history information will be collected to obtain the necessary data and complete the electronic study forms designed for this purpose.

4.9. Study schedule

Study start date (Activation of the first center)	3Q 2020
End date of the study (“Last patient last visit” or end of data extraction)	1T 2021
Study report completion date	2T 2021
Date of first publication	2Q 2021 (expected)

5. VARIABLES

5.1. Study variables

A data collection notebook will be prepared in which the following variables will be collected for analysis:

Affiliation of the center:

- Hospital name
- Province
- Investigator's name
- Patient number

Patient characteristics:

- Age
- Sex
- Age
- Hospital center where the patient is recruited (in order to have epidemiological data on the pandemic that may be of interest)

Pathological history:

- Concomitant pathology (cardiac, pulmonary, renal, liver, Diabetes Mellitus, HIV, AI)
- Usual pharmacological treatment
- Smoking and alcohol habit

Tumor pathology:

- Tumor type, histology and stage (initial and at diagnosis of infection)
- Date of cancer diagnosis
- Active cancer treatment or follow-up
- Participation in clinical trial
- Type of treatment most recently received for the infection (Surgery; Radiotherapy; Chemotherapy: Drug, Immunotherapy, TD: Drug, HT: ADT alone or with Abiraterone, Enzalutamide, others)
- Treatment lines
- Start and last dose received of the most recent oncological treatment

For patients with prostate cancer:

- Local treatment and type (Surgery, Radiotherapy)
- Adjuvant ADT or advanced disease (start date)
- NAH (date and line of treatment)
- Associated corticosteroid treatment: Prednisone vs Dexamethasone (dose)

COVID-19 infection data:

- Confirmation date of COVID-19 infection
- PCR diagnostic test
- IgG or IgM serological diagnostic test
- Present symptoms

- Analytical alterations, lymphopenia, elevated CRP, high D-dimer.
- Thrombosis associated with COVID-19 infection
- Date of onset and disappearance of symptoms
- Days duration of fever and cough
- Radiological examination at the moment of greatest severity
- Complications of infection: presence of complications and/or hospital or ICU admission
- Admission date
- Date of most serious complication
- Treatments received for COVID-19
- Discharge status
- Fecha de alta / exit
- Negativization of the presence of viruses by PCR
- Negative PCR date

For patients who are receiving or have received immunotherapy treatments, additional information will be collected:

- Immunotherapy treatment line
- Start/end date of immunotherapy treatment
- Date of last dose received prior to COVID-19 infection
- Immunotherapy received as monotherapy or combination
- Type of immunotherapy
- Adverse effects

Prospective follow-up data (6 months from patient inclusion):

- Date of start or restart of oncological treatment after infection
- Negative COVID-19 test prior to starting/restarting treatment
- Change/suspension of oncological treatment after COVID-19
- Surgery date in neoadjuvant patients
- Recurrence of COVID-19
- Best answer obtained
- Date of progression to oncological treatment
- Current status
- Last contact date

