3. OBJECTIVES

3.1. Main objectives

- Describe the population infected by COVID-19 with genitourinary tumors (urothelial cancer, prostate cancer, testicular cancer and renal cancer) treated in Spanish hospitals, know the clinical presentation, therapeutic evolution and prognosis of said intercurrent infectious process, as well as its possible relationship with different clinical and therapeutic factors.
- Assess the possible relationship of the different oncological treatments administered to these patients with the clinical evolution of COVID-19 infection, considering both patients who have undergone oncological treatment previously, during or after COVID-19 infection.
- To specifically evaluate the impact of COVID-19 infection on the toxicity of immunotherapy treatment (mainly pneumonitis) and the impact of immunotherapy on the evolution of the infectious condition in patients with tumors of genitourinary origin, in three different scenarios: during treatment, after treatment and in patients who are prescribed treatment after the infection has passed.
- Analysis of this same relationship in patients with genitourinary tumors and asymptomatic COVID-19 infection with positive Ab serologies (IgM and IgG).
- To evaluate in patients with Prostate Cancer (PCa) the impact of androgen deprivation therapy (ADT) and new antiandrogen agents (NAH) with or without corticosteroids on infection COVID-19.

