4. STUDY METHODOLOGY

4.1. Study type and design

This is a national multicenter, observational, retrospective and prospective post-licensure (EPA-AS) study that will include patients with genitourinary tumors presenting with COVID-19 infection.

The study will be carried out in Spanish hospital centers, with principal investigators belonging to the medical oncology services of the SOGUG group (Spanish Genitourinary Oncology Group), who will act as sponsor. Once the patients are selected, the variables described in section 5 of this protocol will be collected and studied.

The study will use data obtained from the patient's medical history, with no plans to use other sources.

The assignment of a patient to a specific therapeutic strategy has already been decided in advance by the usual clinical practice of medicine; The decision to prescribe a specific treatment is clearly dissociated from the decision to include a patient in the study. No intervention, whether diagnostic or follow-up, will be applied to patients other than standard clinical practice. Epidemiological methods will be used to analyze the data collected.

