4.5. Study sample size

The inclusion of a total of 250 patients with genitourinary tumors presenting with COVID-19 infection is expected, sufficient to respond to the objectives set by the study.

Given the characteristics of the study, the total number of patients cannot be previously calculated accurately, although the inclusion of approximately 250 patients is expected. The planned analysis is the descriptive one of each of the variables. The qualitative variables will be compared with each other using the Chi-square test. Quantitative and qualitative analysis using Student's T analysis or ANOVA. If necessary, the corresponding non-parametric tests will be applied. Survival will be calculated using Kaplan-Meyer curves and curve comparison using Log-Rank.

The Statistical Package for the Social Sciences (SPSS) will be used for statistical analyses. Additional analyzes could be performed with other statistical analysis packages.

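### No performance status or other direct functional measure from before infection is collected, so the treatment comparisons would keep residual confounding by fitness, of unknown size, even after adjustment

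*Combined protocol and SAP*

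**What the plan says.** Section 3.1 makes comparison of treatments a main objective. The second objective is to "Assess the possible relationship of the different oncological treatments administered to these patients with the clinical evolution of COVID-19 infection". The third includes the impact of immunotherapy on the infection. The fifth concerns, in prostate cancer, "the impact of androgen deprivation therapy (ADT) and new antiandrogen agents (NAH) with or without corticosteroids". (Section 1.2 numbers these ii, iii and v.)

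Treatment is not randomised. Section 4.1 says: "The assignment of a patient to a specific therapeutic strategy has already been decided in advance by the usual clinical practice of medicine". The same section gives the medical history as the only data source.

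Section 5.1 introduces its list with "A data collection notebook will be prepared in which the following variables will be collected for analysis". For health before infection it has age, sex, "Concomitant pathology (cardiac, pulmonary, renal, liver, Diabetes Mellitus, HIV, AI", "Usual pharmacological treatment" and "Smoking and alcohol habit". For the tumour it has type, histology, stage (initially and when infection was diagnosed), active treatment or follow-up, trial participation, treatment lines and treatment dates. No performance status, frailty or dependence measure, or comorbidity index appears in section 5.1 or elsewhere in the supplied text. Section 5.1 is not redacted.

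Section 4.5 plans chi-square tests, Student's t or ANOVA, non-parametric alternatives, and Kaplan-Meier curves with log-rank tests. It names no stratified or adjusted comparison.

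**The concern.** A patient's fitness before infection plausibly affects both the treatment chosen (chemotherapy, immunotherapy, hormonal treatment or follow-up only) and the chance of admission or death once infected. A treatment given mainly to fitter patients would then look protective, and one given mainly to frailer patients would look harmful, with no true effect.

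The listed variables describe diagnoses, drugs and disease extent. Two patients of the same age, with the same comorbidities, stage and treatment line, can still differ widely in function. An analyst who used every listed variable would have no direct way to separate them.

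The protocol accepts the principle elsewhere. Section 2.2.3 criticises an earlier 28-patient series because its multivariate analysis ignored tumour type and stage.

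The point touches objective ii, the immunotherapy-to-infection part of objective iii, and objective v. The purely descriptive objectives are not affected.

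**Working it through.** **What can be reproduced.** The only stated figure is the sample size. Section 4.5 says "the total number of patients cannot be previously calculated accurately, although the inclusion of approximately 250 patients is expected" and gives no alpha, power, effect size or event rate, so the 250 cannot be re-derived. The finding itself rests on reading the variable list, not on a figure. The rest is illustration, and every input except the total of 250 is an assumption.

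**Illustration 1: mortality mixture, no true treatment effect.**
For a group with a fraction f in poor functional status, mortality is p = (1 − f) × m_good + f × m_poor.

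- Strong imbalance: f = 10% against 40%, m_good = 10%, m_poor = 40%.
  - p1 = 0.90 × 0.10 + 0.10 × 0.40 = 0.13
  - p2 = 0.60 × 0.10 + 0.40 × 0.40 = 0.22
  - OR = (0.13/0.87) / (0.22/0.78) = 0.149/0.282 = 0.53
- Mild imbalance: f = 20% against 30%, m_good = 15%, m_poor = 30%.
  - p1 = 0.80 × 0.15 + 0.20 × 0.30 = 0.18
  - p2 = 0.70 × 0.15 + 0.30 × 0.30 = 0.195
  - OR = (0.18/0.82) / (0.195/0.805) = 0.220/0.242 = 0.91

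**Chance of a significant test.** This uses the normal approximation for two proportions, two-sided alpha 0.05, with an even split of the 250 (250/2 = 125 per group, assumed).

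| Assumed patients per group | 13% against 22% | 18% against 19.5% |
|---|---|---|
| 125 | about 46% | about 6% |
| 40 | about 18% | about 5% |
| 30 | about 15% | about 5% |

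Smaller groups make false significance less likely. They leave the bias in the estimate unchanged.

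**Illustration 2: a second set of assumptions.**
For a true risk ratio of 1 and an unmeasured binary factor that multiplies risk by R, the spurious risk ratio is [1 + q1(R − 1)] / [1 + q0(R − 1)]. Here q1 and q0 are the unfit fractions, with q0 = 20%.

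| R | q1 = 30% | q1 = 40% | q1 = 50% |
|---|---|---|---|
| 1.5 | 1.05 | 1.09 | 1.14 |
| 2 | 1.08 | 1.17 | 1.25 |
| 3 | 1.14 | 1.29 | 1.43 |

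Example: R = 2, q1 = 40% gives 1.40/1.20 = 1.17.

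**Limit on both illustrations.** They are crude. They assume that age, comorbidity, medication, stage and lines capture none of the imbalance, so within each scenario they are upper values for the bias left after adjustment.

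**The case against.** Four objections deserve a hearing.

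- **Fitness is partly measured.** Age, organ-level comorbidity, medication, smoking, stage at infection and treatment lines all carry information about it. This stands. A reader might infer that an odds ratio near 0.53 would survive full adjustment. The documents do not support that: it is a crude figure from assumed inputs that gives the proxies no credit.
- **The 46% is not typical.** No 125/125 split appears in the protocol, and 250 patients are spread over four tumour types and several treatment classes. This stands. The milder scenario rejects about 6% of the time, close to the nominal 5%, and objectives iii and v would use smaller groups.
- **Objective iii is only half affected.** Its other half asks how COVID-19 affects immunotherapy toxicity. The mechanism described here does not fit that question, so it is left out.
- **The study calls itself descriptive (section 6.1), and no adjusted model is planned.** The label does not remove objectives worded as a relationship or an impact. But adding the field alone would change no planned result. The missing adjusted analysis is a separate and larger gap, and this point depends on closing it.

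A reader might also infer that the information would be lost for good. That is too strong, since section 8.2 has investigators keep source documents. Returning to charts at 32 centres would still be costly, with extraction ending in the first quarter of 2021 and the report due in the second (section 4.9).

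**Conclusion.** The point holds as one of residual confounding. Section 5.1 has no direct functional measure from before infection, so the comparisons under objective ii, the relevant half of objective iii and objective v could not be fully corrected for fitness, even by a well-built model on all listed variables.

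The size of the residual is unknown. The crude illustrations run from odds ratios of 0.91 to 0.53, or spurious risk ratios of 1.05 to 1.43. They rest on assumed imbalance, assumed risks and no credit for the proxies. The bias could be slight or serious, in either direction, and the data set as planned offers no direct way to tell which.

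This should be changed because it is cheap, but it ranks below adding an adjusted or stratified analysis.

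**What to change.** Add to section 5.1, under tumour pathology: *ECOG performance status (or Karnofsky, converted) at the last oncology visit before onset of COVID-19 symptoms (or before confirmation if asymptomatic), with date; if none in the chart, code as not recorded.* The value must predate infection so that decline caused by COVID-19 is not entered as baseline.

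Report the proportion not recorded and the interval from assessment to infection. The interval matters most for patients in follow-up only, whose last visit may be old.

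In section 4.5, state that the treatment comparisons named above will be stratified by or adjusted for this variable (0–1, 2 or more, not recorded) together with age, comorbidity, stage and treatment line. Add a sensitivity analysis limited to patients with a recorded value.

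The cost is one or two more abstraction items per patient and a short addition to the analysis text, with no extra visit or procedure. Some charts will have no value, and the documents do not show how many. The gain depends on the stratified or adjusted analysis being added as well.

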3.2. Secondary objectives

- To evaluate the mortality associated with COVID-19 infection in the population with genitourinary tumors. Percentage of patients alive/dead at discharge.
- To evaluate the rate (percentage) of complications that have required hospital admission and/or ICU treatment.
- Describe the frequency of asymptomatic or minimally symptomatic COVID-19 infections. Percentage of asymptomatic patients or with mild symptoms included in the study.
- Evolution of the oncological disease. Impact/influence of COVID-19 infection on the effectiveness of oncological treatment. Data will be collected on delays/modifications in follow-up or oncological treatment regimens. The average delay time and the number of modifications will be evaluated. Likewise, it is expected to obtain data on time to progression and overall survival of cancer patients, which can be compared with the reference values for each type of tumor pathology.

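### Radiology is recorded only at the worst moment and laboratory alterations at no stated time, so their associations with complications, ICU admission or death cannot be read as prognostic

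*Combined protocol and SAP*

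**What the plan says.** Among the infection data in section 5.1 there is one imaging item, "Radiological examination at the moment of greatest severity", and one laboratory item, "Analytical alterations, lymphopenia, elevated CRP, high D-dimer". The laboratory item has no date, cut-off, or rule for choosing between a first and a worst value. Neither item is tied to the confirmation date or the admission date, although both dates are collected. Other items in the same section are anchored: stage is recorded initially and at diagnosis of the infection, and the last immunotherapy dose is the one before infection.

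The first main objective in section 3.1 covers clinical presentation and the "prognosis of said intercurrent infectious process, as well as its possible relationship with different clinical and therapeutic factors". Those factors are not named. Section 4.5 says "The planned analysis is the descriptive one of each of the variables" and continues "The qualitative variables will be compared with each other using the Chi-square test". It does not divide variables into baseline factors and outcomes, and it states no landmark or time-dependent analysis.

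The outcomes available for such comparisons are "Complications of infection: presence of complications and/or hospital or ICU admission" in section 5.1 and "Percentage of patients alive/dead at discharge" in section 3.2.

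**The concern.** A prognostic factor has to be fixed before the outcome develops. The time of the only image on file is chosen by the course of the disease. In a patient who dies it may be close to the last image; in a mild case it may be the only one, or there may be none. If findings accumulate more often in patients who do badly, the worst-point image will differ between outcome groups even when the image at first contact did not.

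The laboratory item has a related weakness. With no rule, one of the 32 centres may enter the presenting value and another the worst value of an admission. Admitted patients are likely to be sampled more often than outpatients, so a worst-value reading would depend partly on admission itself.

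At stake is the interpretation of one class of result. The plan permits a table of imaging and laboratory findings against ICU admission or death, and readers could take it as a list of prognostic markers. No dated presentation value is listed from which to build the table properly.

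**Working it through.** The plan contains no figure to reproduce. The 250 patients in section 4.5 are an expected number, with no alpha, power, effect size or event rate behind them. The check is therefore a reading of the sections side by side, followed by an illustration on assumed rates.

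**Reading**

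1. Imaging time (5.1): the moment of greatest severity. It is known only in retrospect, so it is not a baseline time.
2. Laboratory time (5.1): none given. It may be baseline or not.
3. Imaging at entry (4.3): symptomatic patients need a clinical and/or radiological determination, but 5.1 has no matching dated variable.
4. Use (3.1 with 4.5): prognosis is to be related to unnamed clinical factors, and qualitative variables are compared with each other. Nothing excludes items 1 and 2 as factors.

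**Illustration for imaging.** Only N = 250 comes from the plan; the rest is assumed.

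Let a finding be present at diagnosis in a share b = 0.50 of both survivors and deaths, so that its true prognostic odds ratio is 1.0. Let it newly appear by the worst point in a share g of those still without it. Worst-point prevalence is b + (1 − b)g.

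- Survivors, g = 0.10: 0.50 + 0.50 × 0.10 = 0.55
- Deaths, g = 0.30: 0.50 + 0.50 × 0.30 = 0.65
- Deaths, g = 0.50: 0.50 + 0.50 × 0.50 = 0.75

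Odds ratios:

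- (0.65/0.35) / (0.55/0.45) = 1.52
- (0.75/0.25) / (0.55/0.45) = 2.45

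The chance that a two-sided 5% chi-square test rejects is Φ[(d − 1.96·se₀)/se₁], where d is the difference in prevalence, se₀ the pooled and se₁ the unpooled standard error. At 20% mortality there are 50 deaths and 200 survivors:

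- d = 0.10: se₀ = 0.0783, se₁ = 0.0761; Φ[(0.10 − 0.1535)/0.0761] = Φ(−0.70) = 0.24
- d = 0.20: se₀ = 0.0778, se₁ = 0.0706; Φ[(0.20 − 0.1525)/0.0706] = Φ(0.67) = 0.75

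| Assumed mortality | Rejects at OR 1.52 | Rejects at OR 2.45 |
|---|---|---|
| 10% | 15% | 48% |
| 20% | 24% | 75% |
| 30% | 31% | 86% |

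If new findings are equally common in both groups (g = 0.10 in each), both prevalences are 0.55, the odds ratio stays at 1.0 and the test rejects 5% of the time.

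**Illustration for laboratory values, only if sites record whether a value was ever abnormal.** Assume each draw has probability p of being abnormal, independently and whatever the outcome. Over k draws the chance of at least one abnormal result is 1 − (1 − p)^k. Compare one outpatient draw with eight inpatient draws, both counts being assumptions:

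- p = 0.05: 5% against 1 − 0.95⁸ = 34%
- p = 0.10: 10% against 1 − 0.90⁸ = 57%
- p = 0.20: 20% against 1 − 0.80⁸ = 83%

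Serial draws in one patient are correlated, so independence probably overstates these gaps.

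**The case against.** The strongest reply is that the plan never proposes this use. Neither imaging nor laboratory findings are named as prognostic factors, the analysis is called descriptive, and imaging at the worst moment is a legitimate description of disease course. That is correct: the prognostic use is inferred from 3.1 and 4.5 together. What remains is that nothing in the plan prevents it and no alternative value is listed.

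A reader might go further and infer that these findings are part of the outcome, so that any association is circular or arises by construction. The documents do not support that. The listed outcomes are discharge status, complications, and hospital or ICU admission; imaging and laboratory findings are not listed components of them. The defect is outcome-dependent timing, and as shown above it need not produce an association.

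A reader might also infer that the prognosis part of main objective 1 cannot be answered. That does not follow either. Age, sex, comorbidity, smoking, tumour stage at diagnosis of infection and prior treatment do not depend on the course of the infection. Nor are comparisons of worst-point imaging between treatment groups spoiled in the same way: there the image serves as an outcome, which suits the second main objective.

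The laboratory half is weaker than the imaging half. The item does not state a yes/no format or an ever-abnormal rule, and it follows directly after present symptoms, so presenting values are an open reading. The eight-draw figures have no source in the plan. The one small cancer series described in 2.2.3 (28 patients) had lymphopenia in 82.1% and raised CRP in 82.1%. If first-draw prevalence were that high, repeat sampling could add at most 100 − 82.1 = 17.9 points. Section 5.1 also says the data collection notebook is still to be prepared, so timing may be settled there.

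**Conclusion.** The point holds in a limited form. For imaging, the stated measurement time cannot serve as a baseline, so an association with complications, ICU admission or death cannot be read as prognostic. For laboratory values, the missing time makes the same bias possible but not certain. The other baseline factors are untouched.

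The plan does not allow the size to be estimated. The illustrative odds ratios run from 1.0 to 2.45, and they rest on the assumed 50% prevalence at diagnosis, the assumed rates of new findings and mortality of 10–30%. They show that timing alone can create an apparent association, not that it will do so here. The change is worth making because it is cheap before charts are abstracted and would mean reopening them afterwards.

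**What to change.** In 5.1, add the first radiological examination and the first lymphocyte count, CRP and D-dimer of the COVID-19 episode, each with its date and a 'not done' category. Anchor them as follows:

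- symptomatic patients: symptom onset or first contact;
- asymptomatic patients confirmed by PCR: the date of the positive PCR;
- asymptomatic patients confirmed by serology alone: no baseline value, because the confirmation date may fall well after the infection.

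In 4.5, state that only these first values are used as laboratory or radiological factors for prognosis, and that greatest-severity imaging is kept as a descriptive or outcome variable.

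The cost is a few eCRF fields taken from the same records and a short addition to 4.5. No visit, test or change of care is involved. The drawbacks are extra abstraction time and more 'not done' entries among outpatients, which should be reported as their own category.

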1.2. Methodological aspects

medical product of interest Not applicable
First ethics committee to evaluate the study: Autonomous CEIm of Galicia
Principal Investigators / Coordinators [REDACTED] [REDACTED]

[REDACTED]
 
[REDACTED]
 
[REDACTED]

Researcher/Coordinator Centers:
 
¹ Valencian Institute of Oncology
 
² San Carlos Clinical Hospital of Madrid
 
³ Puerta del Hierro-Majadahonda University Hospital
 
⁴ Lucus Augusti University Hospital, Lugo

Autonomous Communities of Researchers / Coordinators:
 
Valencian Community
 
Autonomous Community of Madrid
 
Galicia

Territorial scope:
 
National, Spain

Information source:
 
Medical records of the patients included after signing informed consent.
 
RETROSPECTIVE PART ONLY: medical records of patients included after signing informed consent or waiver thereof in the cases contemplated (see 6.3 Informed consent).

Type of study (according to the AEMPS classification):
 
EPA-AS

Tracking Type::
 
Ambispective (Prospective and retrospective). A 6-month follow-up is proposed for patients in the prospective part.

Total number of patients expected to include:
 
They are expected to include 250, sufficient to respond to the objectives set by the study.

Planned duration of the study:
 
Data collection 8 months. The estimated duration of the project is 12 to 18 months, depending on the patient inclusion rate.

Study duration for each participant:
 
No specific study visits will be carried out, other than obtaining informed consent in cases where it is required.

Main objectives:
 
a) Main objectives
 
i) Describe the population infected by COVID-19 with genitourinary tumors (urothelial cancer, prostate cancer, testicular cancer and renal cancer) treated in Spanish hospitals, know the clinical presentation, therapeutic evolution and

- prognosis of said intercurrent infectious process, as well as its possible relationship with different clinical and therapeutic factors.
- ii) Assess the possible relationship of the different oncological treatments administered to these patients with the clinical evolution of COVID-19 infection, considering both patients who have undergone oncological treatment previously, during or after COVID-19 infection.

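### Treatment delay, modification, response, progression and post-discharge survival have no listed data source in retrospective survivors, although secondary objective iv is not limited to the prospective part

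*Combined protocol and SAP*

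**What the plan says.** Secondary objective iv (section 1.2, repeated as the last item of section 3.2) concerns the course of the cancer and the effect of COVID-19 on its treatment. On delays and modifications it states: "The average delay time and the number of modifications will be evaluated". It also expects data on time to progression and overall survival. Neither version says which part of the study it covers.

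Section 5.1 groups the variables in blocks. The last block is headed "Prospective follow-up data (6 months from patient inclusion". It contains "Date of start or restart of oncological treatment after infection", "Change/suspension of oncological treatment after COVID-19", the date of surgery in neoadjuvant patients, "Best answer obtained" (evidently best response), "Date of progression to oncological treatment", current status and "Last contact date".

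On who is followed, the tracking-type entry of section 1.2 says: "A 6-month follow-up is proposed for patients in the prospective part". Section 4.1 makes the patient's medical history the only data source for the whole study.

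**The concern.** A site that follows section 5.1 for a patient who had recovered before the centre was activated would complete the baseline, tumour, COVID-19 and, where relevant, immunotherapy blocks. None of these asks what happened to the cancer or its treatment after the infection. Yet the objective is worded for the study as a whole, and the months after infection may already be documented in the chart the site has open.

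Two things are at stake. The first is precision: the number of patients informing this objective is an unplanned fraction of the 250. The second is representativeness: patients infected before the study opened would contribute nothing on delay, modification or progression, and their care may have been disrupted differently. Section 6.3 defends the consent waiver on grounds of representativeness, so the sponsor already regards this as important.

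**Working it through.** **Step 1. Match the objective to the variable list (section 3.2 against section 5.1).**

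| Component of objective iv | Item needed | Listed outside the prospective block? |
|---|---|---|
| Delay | Restart date; surgery date in neoadjuvant patients | No |
| Modifications | Change or suspension after COVID-19 | No |
| Effectiveness of treatment | Best response | No |
| Time to progression | Progression date and a censoring date | No |
| Overall survival | Vital status and date | Only up to discharge (discharge status, discharge or exit date) |

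**Step 2. Look for substitutes in the other blocks.** For every patient, section 5.1 collects whether cancer treatment was active and the dates of the first and last dose of the latest treatment. For immunotherapy patients it adds the start and end dates. These say something about stopping. They do not give a restart, a count of modifications, a response or a progression. Current status and last contact date are also confined to the prospective block, so a retrospective survivor has no follow-up for survival after discharge and no last-contact date for censoring.

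**Step 3. Read the block heading both ways.** The protocol does not define the boundary between the two parts.

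- With section 1.2, the block applies to the prospective part only, and the gap in Step 1 stands.
- On the heading alone, a living, consented patient infected earlier might be followed for 6 months from inclusion. A patient included *k* months after confirmation would then be observed from month *k* to month *k* + 6 after infection, with *k* differing between patients. The heading does not say whether the first *k* months are to be searched, and these are the months in which a delay is most directly tied to the infection.

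**Step 4. Size.** Section 4.5 expects about 250 patients and gives no precision target, power or effect size, so there is no planned figure to reproduce. The retrospective share *R* is not stated and is assumed here.

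Patients carrying the data: n = 250 × (1 − R). Worst-case 95% half-width for a proportion: 1.96 × √(0.25/n).

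| R (assumed) | n | Half-width |
|---|---|---|
| 0 (everyone has the data) | 250 | 1.96 × 0.0316 = 6.2 points |
| 50% | 125 | 1.96 × 0.0447 = 8.8 points |
| 70% | 75 | 1.96 × 0.0577 = 11.3 points |
| 80% | 50 | 1.96 × 0.0707 = 13.9 points |

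These figures are the best precision attainable at each share. Patients who died of COVID-19, or who were off treatment, have nothing to delay or modify, so the real denominators are smaller in every row.

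**Step 5. Is a small prospective part plausible?** Section 1.2 gives 8 months of data collection. If that includes follow-up, 8 − 6 = 2 months remain in which to enrol prospective patients who can complete it. Section 4.9 runs from 3Q 2020 to the first quarter of 2021, at most nine months, leaving 9 − 6 = 3. This makes a minority share plausible but does not establish one.

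**The case against.** The strongest reply is that the text is ambiguous rather than plainly deficient. The two parts are undefined, the block counts from inclusion, and the consent waiver in section 6.3 covers only patients who died before the study was authorised. Living retrospective patients would be asked for consent and could be followed. The eCRF is not among the documents, so what sites would be asked to enter is inferred from section 5.1. This stands in part, and it limits how firmly one can say what sites would do. It does not remove the point: section 1.2 ties follow-up to the prospective part, and the looser reading still starts the clock at inclusion rather than infection.

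A second reply is that the objective is secondary, the planned analysis is descriptive, and the objective's wording on progression and survival is only an expectation. That is fair and bears on severity.

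A reader might infer that objective iv has no measurement at all in retrospective patients. The documents do not support that, because death up to discharge is collected for everyone and the last-dose and immunotherapy end dates give limited information on stopping. A reader might also infer that the results will be biased by a known amount, or presented as if they described the whole cohort. The documents give no modification rates for either part and no reporting rule, so neither can be claimed.

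**Conclusion.** The point holds in a bounded form. As written, retrospective survivors have no listed source for delay, modification, response, progression or vital status after discharge, while the objective carries no such restriction. The placement of the variables is explicit. The remaining doubt concerns the undefined boundary between the parts.

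The loss of precision depends entirely on the assumed retrospective share. At 50% to 80%, 125 to 50 patients carry the data, with half-widths of 8.8 to 13.9 points instead of 6.2. These half-widths describe a proportion, such as patients with any modification. They do not apply directly to the mean delay, for which the documents give no standard deviation. Selective coverage of the later period is a reasonable worry, but its direction and size cannot be derived from the documents.

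This should be corrected before data extraction. It affects a secondary objective and leaves the COVID-19 mortality measure at discharge untouched.

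**What to change.** 1. Define the retrospective and prospective parts, and say which patients each block of section 5.1 covers.
2. Move restart date, change or suspension, surgery date, best response, progression date, current status and last contact date to the core list for all patients. The last two are essential: without them time to progression and overall survival cannot be censored in retrospective patients.
3. For retrospective patients, extract these items from the medical record. Use the COVID-19 confirmation date as the common time origin for both parts, a fixed window (for example 6 months, or to the last chart entry if earlier) and censoring at last contact.
4. Report objective iv overall and by part, with the number of patients contributing to each measure.

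If the sponsor prefers not to extend extraction, restate objective iv in sections 1.2 and 3.2 as applying to the prospective part only, and give that part's expected size.

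The cost is protocol and eCRF wording and a few more fields from charts that sites already open. No visits or tests are added. The downside is a little extra extraction time per retrospective patient.
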